# 1 PROTOCOL SYNOPSIS

Study Title: PD-L1 Inhibition as Checkpoint Immunotherapy for NeuroEndocrine Phenotype Prostate Cancer (PICK NEPC)					
Protocol Number	Pro00080869	Phase	II	Type	Interventional
Condition/Disease: Neuroendocrine prostate cancer (NEPC)					
Number of Subjects	18 in stage 1, 49 overall	Duration of Subject Participation		3 years	
Number of Study Centers	3-4	Duration of Study 8 years		Anticipated 12-18 months accrual time per stage, up to 3 years follow up	

Rationale:
 
Neuroendocrine Prostate Cancer
 
Using the SEER database, there are an estimated 180,890 new cases of prostate cancer in the United States in 2016 with an associated 26,120 deaths for that year. Of those cases, most have adenocarcinoma histology with an estimated 586.0 cases per million per year, but there are multiple other non-adenocarcinoma histologies as well. Although a much less common form of prostate cancer, men with neuroendocrine differentiation of their prostate cancer have a much worse prognosis with median overall survival (OS) of 7 months (mo) compared with years in men with adenocarcinoma. Much of the poor survival related to these patients is related to the fact that all the currently approved therapies for metastatic castration resistant prostate cancer (mCRPC) including docetaxel, cabazitaxel, abiraterone, enzalutamide, radium-223, Sipuleucel-T are only proven and effective in patients with adenocarcinoma. Therefore to date there are no phase 3 studies that definitively show an overall survival benefit in men with neuroendocrine differentiation which highlights the need for more effective therapies in these men.
 
Neuroendocrine prostate cancer (NEPC) lies on a spectrum of aggressive prostate cancer along with small cell prostate cancer (SCPC) and was defined originally by histology that was similar to neuroendocrine tumors of other origins. SCPC has classic histologic features such as small tumor cells with scanty cytoplasm, darkly stained nuclei with homogeneous chromatin pattern and do not form glandular structures but grow as solid sheets with frequent mitotic figures and necrosis. Different from SCPC, NEPC has been harder to classify as a group and is now being redefined to be intermediate atypical carcinoma (IAC) of the prostate with histologic features distinct from small cell carcinoma or adenocarcinoma. IAC grows as solid sheets or vague glandular structures, has moderate amounts of cytoplasm and centrally located, round and regular nuclei with fine, granular and homogeneous chromatin. Mitosis and necrosis are absent. NEPC spectra histologies have a very aggressive clinical phenotype and often have low PSA (as these tumors do not make it), predominant visceral spread, osteolytic and not osteoblastic bone lesions, bulky lymphadenopathy, and the development of castration resistance within 6 months of androgen deprivation therapy (ADT). In addition, NEPC tumors have a higher mutational burden than typical adenocarcinoma suggesting an opportunity for immunotherapy in this disease.
 
NEPC can not only be present from the onset of diagnosis but also transform out of treated mCRPC and is likely found in 20-30% of castration-resistant tumors compared to 5-10% at initial diagnosis. Since this treatment-related NEPC is becoming more recognized and common and since it is very resistant to the conventional therapies of mCRPC, new therapies need to be developed for men with this disease.
 
Treatments for NEPC and Study Rationale
 
Currently the standard of care for treating NEPC and its spectrum of diseases is to start with ADT as most NEPCs are mixed with adenocarcinoma. Once the cancer has become CRPC or if the histology at diagnosis was small cell
					

prostate cancer (SCPC), the therapy tends to focus on using platinum combination therapy. Although there are no phase 3 trials looking at these therapies the literature shows that many patients have been treated with cisplatin and etoposide. Although platinum appears to have a benefit in NEPC, none of them have been curative or led to long term remission in the vast majority of men. In mCRPC platinum has been tested alone or in combination with other chemotherapies and the results have shown some dramatic successes with soft tissue response rates in the 70s and 80s in some studies while other have been in the teens. Platinum acts through DNA damage and it is conjectured that patients with inherited DNA-repair gene mutation, which is approximately 12% of metastatic prostate cancer, or acquired DNA-repair gene mutations may benefit from them as shown in the TOPARP trial, a single arm phase II trial that showed that patients with mCRPC that had DNA-repair defects had better survival and response rates to olaparib a poly(adenosine diphosphate [ADP]-ribose) polymerase inhibitor.

Immune checkpoint blockade is a novel systemic approach in which the patient's own immune system is stimulated to better recognize and destroy cancer cells. Ipilimumab and nivolumab, blocking monoclonal antibodies to CTLA-4 and programmed-death receptor-1 (PD-1) respectively, acts to over stimulate the immune system and both have been studied in melanoma both as single agents and in combination to improve the overall survival of patients with melanoma.

Although the small cell histology is rare in prostate cancer, it is common in lung cancer. Small cell lung cancer (SCLC) like that of the prostate has a poor overall survival. Currently the mainstay of chemotherapy in SCLC is combination cisplatin with etoposide which is where SCPC got the direction to be treated by these agents given the similarity of histology. Recently a phase 1/2 trial was performed that enrolled patients with progressive lung SCLC to nivolumab with and without ipilimumab in varying dose combinations. The results demonstrated that the nivolumab alone arm had 15% with partial response and 22.5% with stable disease compared to 5% (1 patient) with a complete response, 20% with partial response, and 30% with stable disease in the combination arm. Not only were there responses in each arm, some appeared to be durable. These data suggest efficacy of PD-1 inhibition in patients with neuroendocrine lung cancers.

#### **Avelumab**

Avelumab is a fully human antibody that specifically targets and blocks PD-L1, thus removing the suppressive effects of PD-L1 on the anti-tumor CD8+ T cells. It has been studied in Phase I and II trials including patients with non-small cell lung cancer, ovarian cancer, and Merkel cell carcinoma. The NSCLC expansion cohort had an objective response rate (ORR) of 14.1% (26 of 184 NSCLC subjects). An ovarian cancer expansion cohort had an ORR of 10.7% (8 of 75 subjects). The Phase II trial in Merkel Cell carcinoma gave avelumab to 88 patients and resulted in an objective response in 31.8%, including 8 complete responses.

Data supporting PD-L1 inhibition in prostate cancer was found when enzalutamide resistant cell lines and xenografts on mice had increased PD-L1. Our own cell lines established at Duke that are enzalutamide resistant also demonstrate upregulation of PD-L1 at the protein and RNA level as compared with the parental cell lines, suggesting that PD-L1 is an adaptive response to stress and is highly dynamic (data unpublished). Further, we have also looked at a cohort of patients with NEPC/SCPC using a tissue microarray for PD-L1 expression by immunohistochemistry and have found that a small subset (~20% small cell, ~10% adenocarcinoma) of these cases express high levels of PD-L1 (data unpublished). Further still is evidence showing that there is a high burden of genetic mutations in NEPC which has been seen in other cancers to confer susceptibility to immunotherapy.

Given the emerging role of immunotherapy across multiple tumor types to produce durable responses, and given the similarity of small cell by both histology and its response to current chemotherapy, we hypothesize that avelumab will produce a clinical and radiographic response in NEPC that will be durable in a subset of patients. In this study, we are defining the NEPC "phenotype" based on clinical poor risk features of AR-independence or based on histologic evidence of NEPC in tissue or serum.

**Primary Objective:** To determine the efficacy of PD-L1 inhibition with avelumab as measured by a modified PCWG3, where RECIST 1.1 is replaced with iRECIST, a modified RECIST 1.1 for immune-based therapeutics, radiographic response rate in men with metastatic neuroendocrine-like prostate cancer.

**Secondary Objectives:**

1. To describe the efficacy of PD-L1 inhibition with avelumab as measured by PCWG3 using RECIST1.1
2. To describe the radiographic progression free survival (rPFS) of PD-L1 inhibition with avelumab using modified PCWG3 with both RECIST 1.1 and iRECIST criteria in this setting.
3. To describe the overall survival of PD-L1 inhibition in this setting.
4. To describe the toxicities and safety of PD-L1 inhibition with avelumab in men with metastatic neuroendocrine-like prostate cancer.

**Exploratory Objectives:**

1. To describe the impact of PD-L1 inhibition with avelumab on blood-based biomarker changes over time, including PSA, chromogranin-A, cell free DNA, LDH, and alkaline phosphatase.
2. To determine if levels of circulating biomarkers secreted by neuroendocrine-like prostate cancers correlate with clinical and radiographic treatment response
3. To determine if the presence of different immunohistochemical markers on the pre-biopsy specimens prognosticates clinical and radiographic treatment response
4. To determine if the level of different circulating immune cells correlate with both progressive addition of immunotherapy as well as clinical and radiographic treatment response or disease progression
5. To determine if levels of cell free DNA correlate with clinical and radiographic treatment response
6. To isolate prostate neuroendocrine-like CTCs for ex vivo growth and culture and characterization studies.

**Hypothesis:**

We hypothesize that PD-L1 inhibition with avelumab will be efficacious based on radiographic responses in a subset of men with metastatic neuroendocrine-like prostate cancer and be reasonably well tolerated, meeting criteria for further study in larger phase 2 and 3 trials based on meeting pre-specified efficacy rates and prolonged PFS in some men.

**Design:**

This is a phase 2, open-label, single arm trial of avelumab in men with metastatic neuroendocrine-like prostate cancer. Men who meet inclusion criteria (without exclusions) will be started on avelumab 10 mg/kg IV every 2 weeks and will stay on therapy until progression or intolerable side effects. Cycles will be 4 weeks long and thus include 2 doses of avelumab. Baseline tissue will be assessed histologically for eligibility at Duke and for correlative tissue biomarkers. Treatment beyond radiologic or PSA progression is permitted after approval of the PI of the study and if the providing physician and patient determine that there is potential for clinical benefit with continued therapy.

At radiologic progression a standard of care post-treatment progression biopsy will be collected at the discretion of the treating provider, and if proper consent is obtained, additional tissue will be collected for research tests including assessments of resistance mechanisms and immune checkpoint status. The additional research tissue will be banked in the Biospecimen Repository & Processing Core (BRPC) under Pro00080869. The study team will also pursue dual consent to BRPC Pro00035974 for future unspecified research.

Men will continue on their ADT used at entry into study per investigator with subsequent changes made per investigator. Men not on ADT at time of entry due to being purely SCPC may remain off ADT. Men with SCPC on ADT at study entry should remain on ADT per investigator while all men with mixed histologies should remain on active ADT during trial participation.

Men will be allowed to receive palliative radiation to any disease site indicated by the treating physician at any time during the study, provided that another untreated site of measureable disease is present at baseline. All subjects will be followed for disease progression and mortality for up to 3 years from the date that the subjects were enrolled to the protocol.

**Study Population:** This is a non-blinded single arm-arm phase II study of approximately 49 subjects, to assess the safety and efficacy of avelumab in patients with mCRPC. Eligible men will have metastatic CRPC with NEPC phenotype with measureable disease at baseline.

The target sample size is 18 in stage 1, and overall 49 evaluable subjects. For stage 1, Duke will serve as the single site for this study. For stage 2, the study would be expanded to include additional sites through the Department of Defense Prostate Cancer Clinical Trials Consortium (DOD PCCTC). All subjects will be followed for disease progression and death from the date that the subjects were enrolled to the protocol.

**Selection of Subjects:**Inclusion Criteria:

1. Neuroendocrine-like prostate cancer, based on histology OR based on clinical presentation as defined by meeting one of the two below criteria. All subjects must submit their primary tumor or metastatic biopsy pathology specimens to the Duke Cancer Institute where they will be centrally reviewed by Duke Pathology ([name]). Central Duke pathologic review is not required for screening but rather for confirmation of histologic subtype. Local pathologic review is sufficient for eligibility determination.
  - a. **Criterion 1:** Presence of 1 of 3 histologically proven diagnoses: **1)** Primary small cell carcinoma of the prostate, defined by classic histologic features such as small tumor cells with scanty cytoplasm, darkly stained nuclei with homogeneous chromatin pattern. The tumor cells do not form glandular structure but grow as solid sheets with frequent mitotic figures and necrosis; **2)** Intermediate atypical carcinoma of the prostate, which has histologic features distinct from small cell carcinoma or adenocarcinoma. The tumor grows as solid sheets or vague glandular structures. The tumor cells have moderate amounts of cytoplasm and centrally located, round and regular nuclei with fine, granular and homogeneous chromatin. Mitosis and necrosis are absent; **3)** mixed histology tumors of the prostate, containing both adenocarcinoma and neuroendocrine or small cell components.

- b. **Criterion 2:** Presence of histologically proven adenocarcinoma of the prostate without any sign of neuroendocrine or small cell histology that is radiographically progressing despite castrate levels of testosterone (<50 ng/mL) with the following poor risk features:
  - i. Prior progression despite therapy with either abiraterone acetate and/or enzalutamide
  - ii. At least one of the following: 1) Liver metastases; 2) Bulky radiographic progression ( $\geq 2$  cm short axis lymph nodes or  $\geq 1$  cm long axis visceral metastases) combined with low serum PSA (<10ng/mL); 3) High serum LDH (>1X upper limit of normal).
- 2. Measurable disease as defined by modified PCWG3 using iRECIST criteria
- 3. Available tumor tissue for pathologic review and correlative studies. Tumor tissue (localized or metastatic) does not need to be received but rather identified and available (slides and/or blocks) to be sent to Duke.
- 4. Documented progressive metastatic CRPC based on at least one of the following criteria:
  - a. PSA progression defined as 25% increase over baseline value with an increase in the absolute value of at least 2.0 ng/mL that is confirmed by another PSA level with a minimum of a 1 week interval and a minimum PSA of 2.0 ng/mL. Note: If confirmed rise is the only indication of progression, a minimal starting value of 1.0 ng/mL is acceptable, unless pure small-cell carcinoma.
  - b. Soft-tissue progression based on new lesions or growth of existing soft tissue metastases.
  - c. Progression of bone disease (evaluative disease) or (new bone lesion(s)) by bone scan.
- 5. Castrate levels of serum total testosterone ( $\leq 50$  ng/dl) OR ongoing documented ADT unless pure small cell prostate cancer is present.
- 6. Previous use of radiation to metastatic site(s) at any time prior to enrollment is allowed, provided that this site is not the only measurable disease present or unless that solitary site is progressing following radiation.
- 7. Patients should have received at least one line of approved chemotherapy and/or hormonal therapy
- 8. Previous cytotoxic chemotherapy including cisplatin, carboplatin, oxaliplatin, etoposide, docetaxel, cabazitaxel, and gemcitabine is allowed, up to 3 prior regimens.
- 9. Karnofsky performance status of 70 or higher.
- 10. Acceptable initial laboratory values within 14 days of Cycle 1 Day 1 according to the below table:

ANC	$\geq 1500/\mu\text{l}$
Hemoglobin	$\geq 9.0$ g/dL (prior transfusion is permitted)
Platelet count	$\geq 100,000/\mu\text{l}$
Creatinine	$\leq 2.0$ x the institutional upper limit of normal (ULN) OR creatinine clearance $>30$ ml/min
Potassium	$\geq 3.5$ mmol/L (within institutional normal range)
Bilirubin	$\leq 1.5$ x ULN (unless documented Gilbert's disease)
SGOT (AST)	$\leq 2.5$ x ULN, or $\leq 5$ x ULN in patients with documented liver metastases
SGPT (ALT)	$\leq 2.5$ x ULN or $\leq 5$ x ULN in patients with documented liver metastases

- 11. Age  $\geq 18$
- 12. Highly effective contraception for male subjects with childbearing potential throughout the study and for at least 60 days after last avelumab treatment administration if the risk of conception exists.
- 13. Willing and able to provide written informed consent and HIPAA authorization for the release of personal health information.
- 14. Life expectancy of over 3 months as determined by treating physician.

Exclusion Criteria:

- 1. Prior usage of PD-1 inhibitors, programmed-death ligand 1 and/or 2 inhibitors, CTLA-4 inhibitors including but not limited to ipilimumab, nivolumab, avelumab, durvalumab, tremelimumab, and pembrolizumab.

2. Active on-going immunologic or autoimmune disease including but not limited to systemic or cutaneous lupus erythematosus, cutaneous psoriasis, psoriatic arthritis, rheumatoid arthritis, scleroderma, sicca syndrome, polymyalgia rheumatica, polyarteritis nodosa, granulomatous polyangiitis, microscopic polyangiitis, polyarteritis nodosa, temporal arteritis, giant cell arteritis, dermatomyositis, Kawasaki disease.
3. Previous malignancy within 3 years other than non-melanomatous skin cancers or cancers of low malignant potential such as non-invasive urothelial carcinoma.
4. Any other on-going chemotherapeutic, biologic, radiopharmaceutical, or investigational agent currently or within 28 days of cycle 1 day 1.
5. Prior use of abiraterone and other hormonal agents used to treat prostate cancer are permitted but abiraterone acetate should be stopped prior to study treatment initiation.
6. Current usage of immunosuppressant medication except for a) intranasal, inhaled, and topical corticosteroids and b) systemic corticosteroids equivalent to  $\leq 10$  mg/day of prednisone, c) steroids as premedication for hypersensitivity reactions (e.g. CT scan premedication).
7. Prior organ transplantation including allogeneic stem-cell transplants.
8. Active bacterial or viral infections requiring systemic therapy.
9. Current active infections with HIV/AIDS, Hepatitis B, and Hepatitis C requiring treatment.
10. Live virus vaccination within 4 weeks of the first dose of avelumab (inactivated vaccines are allowed).
11. Known prior hypersensitivity to the investigational product or any component formulations, including known severe hypersensitivity reactions to monoclonal antibodies.
12. Clinically significant (i.e. active) cardiovascular disease: cerebral vascular accident (<6 months prior to enrollment), myocardial infarction (<6 months prior to enrollment), unstable angina, congestive heart failure ( $\geq$  New York Heart Association Classification Class II), or serious cardiac arrhythmia requiring medication.
13. Persisting toxicity related to prior therapy (NCI CTCAE v. 4.03 Grade  $> 1$ ); however, alopecia, sensory neuropathy Grade  $\leq 2$ , Grade 2 anemia, or other Grade  $\leq 2$  not constituting a safety risk based on investigator's judgment are acceptable.
14. Other severe acute or chronic medical conditions including colitis, inflammatory bowel disease, pneumonitis, pulmonary fibrosis or psychiatric conditions including recent (within the past year) or active suicidal ideation or behavior; or laboratory abnormalities that may increase the risk associated with study participation or study treatment administration or may interfere with the interpretation of study results and, in the judgment of the investigator, would make the patient inappropriate for entry into this study.

**Study Intervention and Administration:**

The study agent avelumab will be administered at a dose of 10 mg/kg by IV every 2 weeks until progression or intolerable side effects. Cycles will be 4 weeks long and thus include 2 doses of avelumab. In order to mitigate infusion related reactions, a premedication with an antihistamine and with paracetamol (acetaminophen) 30 to 60 minutes prior to each dose of avelumab is mandatory. Avelumab should be administered in a setting that allows for immediate access to an intensive care unit or equivalent environment and administration of therapy for anaphylaxis, such as the ability to implement immediate resuscitation measures. Avelumab should be given over 2 hours (-10 min/+20min). Steroids (dexamethasone 10 mg), epinephrine (1:1,000 dilution), allergy medications (IV antihistamines), bronchodilators, or equivalents, and oxygen should be available for immediate access. Following avelumab infusions, subjects must be observed for 30 minutes post infusion for potential infusion related reactions. Avelumab will be provided by Pfizer and distributed by DCI Investigational Chemotherapy Service.

**Study Assessments:**

Vital signs, performance status, physical exam, adverse events and concomitant medications will be assessed at each visit. The following laboratory studies will be obtained at intervals specified in the study flow chart to assess subject safety: complete blood count, serum chemistries, TSH and free T4. Testosterone, blood-based biomarkers (such as PSA, CEA, chromogranin A, etc), immune cells, and cell free DNA will also be assessed for disease status and correlative science. A bone scan and either CT or MRI scans of the chest, abdomen, and pelvis will be performed to assess disease status at baseline as well as every 8 weeks or at treatment discontinuation. Patient reported outcomes will be collected using the Functional Assessment of Cancer Therapy – Prostate (FACT-P) at baseline and

[figure not shown]
every 3 cycles to assess quality of life. The pre-biopsy specimen obtained during screening and the optional post-progression biopsy will be assessed for correlative biomarkers and resistance mechanisms.

**Data Analysis and Statistical Considerations:**

This study will use the optimal two-stage Simon design to test the hypothesis about modified PCWG3 using iRECIST radiologic response rate in subjects with NEPC treated with avelumab. Response will be defined as a complete (CR) or partial response (PR) using iRECIST criteria. Assuming that the response rate among subjects treated is 5%, the trial is designed to have 88% power with a one-sided type I error rate=5% to reject the null hypothesis of response rate of 5% when the true response rate was 20%. In the first stage, 18 subjects will be enrolled and if one or fewer responses are observed the trial will be terminated. However, if two or more responses are observed, an additional 26 subjects will be enrolled at the second stage for a total of 44 subjects. If five or more subjects respond, this new agent would be declared to have promising activity. This design has 88% power to conclude an agent is promising if its true objective response proportion is 20%; Type 1 error rate (one-sided) is 0.05 (this is the probability to conclude that a given agent is promising if its true objective response proportion is 5%). The probability of early termination under the null hypothesis is 0.77. These operating characteristics were selected to represent a reasonable compromise between high power, low false positive rates, and desire for small sample sizes, especially in the first stage. Allowing for 10% unevaluable rate, the target sample size is 49 subjects.

With 44 subjects, the objective response rate will be estimated with a standard error no greater than 10.7 percentage points. The Kaplan-Meier method will be used to estimate progression-free survival and overall survival distributions. Summary statistic will be computed for the duration of time on treatment distribution. The correlative science analyses will be considered exploratory and interpreted as such.

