## 5.10 Definition of Evaluable Subjects, On Study, and End of Study

Patients who consent but do not receive a dose of study drug will be replaced and will not be considered evaluable.

All subjects enrolled onto the study who receive at least one dose of avelumab will be included in the intention-to-treat analysis for the primary endpoint.

All subjects enrolled onto the study who receive at least one dose of avelumab will be evaluable for the secondary and exploratory endpoints.

Given the potential risk for delayed immune-related toxicities, safety follow-up must be performed 28 days after the last dose of avelumab administration.

The extended safety follow-up beyond 28 days after last study drug administration may be performed either via a site visit or via a telephone call with subsequent site visit requested in case any concerns noted during the telephone call.

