### 11.1 Sample Size Estimation

This study will use the optimal two-stage design of Simon to test a hypothesis about response rate in subjects with NEPC treated with avelumab. Response will be defined as a complete (CR) or partial response (PR). Assuming that the response rate among subjects treated is 5%, the trial is designed to have 88% power with a one-sided type I error rate=5% to reject the null hypothesis of response rate of 5% when the true response rate was 20%. In the first stage, 18 subjects will be enrolled and if one or fewer responses are observed the trial will be terminated. However, if two or more responses are observed, an additional 26 subjects will be enrolled at the second stage for a total of 44 subjects. If five or more subjects respond, this new agent would be declared to have promising activity. This design has 88% power to conclude an agent is promising if its true objective response proportion is 20%; Type 1 error rate (one-sided) is 0.05 (this is the probability to conclude that a given agent is promising if its true objective response proportion is 5%). The probability of early termination under the null hypothesis is 0.77. These operating characteristics were selected to represent a reasonable compromise between high power, low false positive rates, and desire for small sample sizes, especially in the first stage. Allowing for 10% unevaluable rate, the target sample size is 49 subjects.

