### 11.5.2 Statistical Hypothesis, Model, Method of Analysis

The null hypothesis is that the ORR is less than 5%. The trial is designed to have 88% power with a one-sided type I error rate=5% to reject the null hypothesis when the true response rate was 20%. The objective response rate will be estimated with a standard error no greater than 10.7 percentage points.

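### The stated bound on the standard error of the response rate, 10.7 points with 44 subjects, does not match that sample size: the maximum is 7.54 points

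*Combined protocol and SAP*

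**What the plan says.** The synopsis, under Data Analysis and Statistical Considerations, states: "With 44 subjects, the objective response rate will be estimated with a standard error no greater than 10.7 percentage points". Section 11.5.2 says the same for the primary analysis but names no sample size: "The objective response rate will be estimated with a standard error no greater than 10.7 percentage points". Neither place gives a formula, an assumed response rate or a confidence level.

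The 44 comes from the two-stage design in the synopsis and section 11.1. On stage 1: "In the first stage, 18 subjects will be enrolled and if one or fewer responses are observed the trial will be terminated". If the trial continues, "an additional 26 subjects will be enrolled at the second stage for a total of 44 subjects". On the final decision: "If five or more subjects respond, this new agent would be declared to have promising activity". Section 11.1 then inflates the number: "Allowing for 10% unevaluable rate, the target sample size is 49 subjects".

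Other places describe the analysed number differently. The Study Population text of the synopsis says: "The target sample size is 18 in stage 1, and overall 49 evaluable subjects". Section 5.10 says that enrolled subjects "who receive at least one dose of avelumab will be included in the intention-to-treat analysis for the primary endpoint".

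**The concern.** A precision statement that names only a sample size is normally read as the worst case over all response rates, and a figure given to one decimal reads as calculated. For 44 subjects that calculation gives about 7.5 points, not 10.7. A reader who checks the sentence cannot tell whether the standard error or the sample size is wrong.

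This is the plan's only numerical statement of precision for the primary endpoint, and it appears twice. If it stays, the trial is described as less precise than it will be. It could also suggest a slip elsewhere in the design calculations, so those were checked too.

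**Working it through.** **Inputs.** From the synopsis and section 11.1: stage 1 n = 18, stop at 1 or fewer responses; stage 2 n = 26; total 44; promising at 5 or more responses; null rate 5%, alternative 20%; enrolment target 49. From section 11.5.1: the endpoint is binary (CR or PR). Stated bound: 10.7 points.

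**1. Trying to reproduce 10.7.** The standard error of an observed proportion is sqrt(p(1 − p)/n), largest at p = 0.5, where it equals sqrt(0.25/n).

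| n | Role in the plan | Maximum SE (points) |
|---|---|---|
| 18 | stage 1 | 11.79 |
| 22 | none | 10.66 |
| 26 | stage 2 | 9.81 |
| 44 | design total | 7.54 |
| 49 | enrolment target | 7.14 |

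Solving backwards, 0.25/0.107² = 21.8. Allowing for rounding (10.65 to 10.75), n lies between 21.6 and 22.04, so 10.7 is the maximum for 22 subjects.

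Other readings with 44 subjects also fail:
- Divisor n − 1: sqrt(0.25/43) = 7.62.
- Maximum half-width of a confidence interval: 9.66 (80%), 12.40 (90%), 14.77 (95%).
- A 90% half-width at a 25% response rate is 10.74. This is neither a standard error nor a maximum, and 25% is not a design rate.

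With 18 subjects, 10.7 occurs at a response rate of 29%, but it is not the maximum there.

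**2. Allowing for the stage 1 stop.** All outcomes of the two-stage design were enumerated. The estimate is x/18 if the trial stops and (x + y)/44 otherwise. The standard deviation of this estimate, maximised over the true rate, is 7.55 points (at about 49%). With a total of 49 it is 7.16 points (at about 23%). If the trial does stop, the estimate is at most 1/18, with estimated standard error at most sqrt((1/18)(17/18)/18) = 5.40 points.

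**3. Size of the discrepancy.** 10.7/7.54 = 1.42.

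At the design rates with a fixed n of 44:
- 20%: sqrt(0.20 × 0.80/44) = 6.03 points.
- 5%: sqrt(0.05 × 0.95/44) = 3.29 points.

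Under the two-stage rule the corresponding values are 7.31 and 3.62 points. All are well below 10.7.

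**4. Rounding of a replacement.** Estimated standard error with 44 subjects, by number of responses:

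| Responses | 19 | 20 | 21 | 22 | 23 | 24 | 25 |
|---|---|---|---|---|---|---|---|
| SE (points) | 7.467 | 7.507 | 7.530 | 7.538 | 7.530 | 7.507 | 7.467 |

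A strict bound of 7.5 would be breached at 20 to 24 responses. A bound of 7.6 is never breached.

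**5. The rest of the design.**
- Early termination at 5%: 0.95^18 + 18 × 0.05 × 0.95^17 = 0.7735 (stated 0.77).
- Probability of declaring the agent promising, summed over stage 1 counts of 2 or more: 0.0495 at 5% (stated 0.05) and 0.8806 at 20% (stated 88%).
- Inflation: 44/0.9 = 48.9, rounded up to 49.

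All of these reproduce, so 10.7 is an isolated figure.

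**The case against.** The strongest reply is that the sentence is true. It says no greater than 10.7 and does not call that the maximum; 7.54 is below 10.7 at every response rate. The looseness is on the cautious side, so nobody could overclaim precision from it, and no decision uses it. All of this stands, and it is why the point is minor. It does not justify the figure: a bound that 44 subjects cannot approach at any response rate does not tell the reader what 44 subjects deliver, and no derivation is given.

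It is also fair that the origin is unknown. The match to 22 subjects is arithmetic, not an explanation of how the figure arose.

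A further objection is that 7.6 depends on the number analysed and on the divisor. With 43 subjects the maximum is 7.62, and with 44 and an n − 1 divisor it is also 7.62. That is correct, and it is a reason to attach the figure to its n and formula. It does not weaken a bound stated for 44 subjects with divisor n.

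Finally, whether 44 or 49 subjects are evaluable is a separate, analysis-set question that cannot account for 10.7, since 49 subjects give 7.14. That too is right. It matters here only because section 11.5.2 names no n.

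**Conclusion.** The concern holds, as a minor arithmetic error in a precision statement. The worst-case standard error with 44 subjects is 7.54 points (7.55 with the stage 1 stop), against a stated 10.7, so the stated bound is about 42% too large. It is not the maximum for any sample size in the efficacy design. The sentence remains literally true, and the discrepancy understates the trial's precision.

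The conclusion assumes the usual binomial standard error of the observed proportion, with 44 subjects as the synopsis states. It would not change with 49 subjects (7.14, or 7.16 with the stage 1 stop). The design's operating characteristics are unaffected.

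**What to change.** In the synopsis (Data Analysis and Statistical Considerations) and in section 11.5.2, replace 10.7 by 7.6 percentage points. In section 11.5.2, add that the figure is for 44 subjects, preferably with the formula: sqrt(0.25/44) = 7.54. Do not round down to a strict bound of 7.5. The 7.6 also covers 49 analysed subjects and the two-stage estimate; if fewer than 44 are analysed, recompute it from the formula.

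In the same revision, settle which number is the evaluable one. The synopsis Study Population text calls 49 evaluable, while section 11.1 reaches 49 by adding an unevaluable allowance to 44. Section 5.10 includes every dosed subject in the primary analysis, whereas sections 8.11.4 and 11.5.3 restrict the analysis to eligible subjects. The correction to the standard error does not depend on the outcome.

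The cost is one number in two places, a few words in section 11.5.2, and a wording change on evaluability in the synopsis, with section 5.10 aligned if needed. The design, sample size and decision rule stay as they are.
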